2.3 Study Design

Type of study: A multi-centre, cross-sectional study of four questionnaires including clinic data.

Duration of the study: 12 months.

Sample size: 80 – 107 participants from each of the three centres (N= 240 - 321):

Royal Brompton and Harefield NHS Foundation Trust, London, UK

Birmingham Heartlands Hospital NHS Foundation Trust, Birmingham, UK

University Hospital of South Manchester, Manchester University NHS Foundation Trust, UK

Royal Devon and Exeter Hospital NHS Foundation Trust, Exeter, UK

2.4 Study outcome measures

2.4.1 Questionnaires:

Severe Asthma Questionnaire (SAQ) (Appendix 2)

The new questionnaire will provide a combined assessment of disease and its treatment on the quality of life of patients with severe asthma. The scale is based on existing HRQoL scales but modified for the severe population and provides separate assessments of the effect of asthma symptoms and the effect of asthma medicines. The questionnaire has 16 items and was produced from detailed qualitative research. An additional 3 items are included to assess overall QoL, and QoL during different months of the year [13].

EQ-5D-5L (Appendix 3)

This is a 5-item scale, with a final question which asks patients to use a category rating scale to rate their quality of life on the day of completion. This scale is commonly used in clinical trials to determine improvement in patients' perceived quality of life. The correlations between EQ-5D-5L scores and SAQ scores will be explored [14].

Routine Clinic Questionnaires**The Mini Asthma Quality of Life Questionnaire (MiniAQLQ) (Appendix 4)**

This 15-item scale is commonly used as the quality of life scale in asthma studies [15]. For the purpose of validation, we wish to show that this scale correlates with the burden of symptoms but not, or with a much lower correlation, with the burden of treatment.

Asthma Control Test (ACT) (Appendix 5)

This 5-item scale is commonly used as a measure of asthma control in asthma studies [16]. For the purpose of validation, we wish to show that this scale correlates with the burden of symptoms but not, or with a much lower correlation, with the burden of treatment.

OR (depending on the preference of centres)**Asthma Control Questionnaire (Asthma Control Questionnaire) (Appendix 6)**

Another questionnaire of asthma control. This questionnaire contains 7 items and takes into consideration FEV1% predicted and daily use of rescue bronchodilator. Patients respond to 7 items concerning their symptom severity on a 0-6 scale (0 = no impairment, 6 = maximum impairment) [17]

2.4.2 Clinic Data to be collected:

Data to describe patient characteristics

Patient demographics:

Age
Sex
Ethnicity

Clinical data:

Spirometry: absolute Forced Expiratory Volume (FEV1) (litres) and percentage of predicted FEV1 (FEV1%)
Forced Vital Capacity (FVC) (litres)
Weight (Kg), Body Mass Index (BMI)
Asthma severity: Treatment level by drug class classified by GINA step

Health care utilisation:

Emergency Department, attendance in the last 12 months
Hospital admissions in the last 12 months

Clinic Data Outcome Measures:

Number of exacerbations in the last 12 months requiring OCS

Prednisolone dose mg / day if on maintenance OCS

Note: The three UK specialist centres are part of the BTS severe asthma network, and contribute to a shared database. Except for the two study questionnaires (SAQ and EQ-5D-5L) the above data are part of routine data collection.

Permissions will be obtained following procedures appropriate for each centre.

2.5 Patient Invitation Letter and Patient Information Leaflet

As this study is taking place at multiple sites, the Patient Invitation Letter and Information Leaflet will need to be adapted for use by each centre. The anticipated adaptations will include: letter heading; and a change of the centres PI and research nurse contact details in the case that a participant has questions.

2.6 Recruitment and consent.

Patient eligible to participate in the study will be identified by a health care professional familiar with them. When possible, a Patient Invitation Letter (Appendix 7) and a Patient Information Leaflet (Appendix 8) will be posted to eligible patients two weeks before their scheduled clinic appointment. The Invitation Letter and Information Leaflet will provide patients with instruction to read the information carefully and to decide if they wish to participate in the study. The Information Leaflet will contain contact details for the patients clinical care team, as well as the SAQ development team in case the patient has questions. If they understand the information they have read and wish to participate, the Information Leaflet asks patients to sign the consent form and bring it with them to their next scheduled clinic appointment.

Alternatively, patients will be approached by a member of their clinical care team and asked if they wish to participate in the study during a clinic appointment. Patients will be provided with a Patient Information Leaflet at this time and given time to read through it and have any questions answered by *either* a healthcare professional responsible for their care before consenting *or* a member of the SAQ development team. When ready, the patient will be asked to sign the Consent Form.

The right of the participant to refuse to participate without giving reasons will be respected. All participants are free to withdraw at any time from without giving reasons and without prejudicing further treatment.

2.6.1 Inclusion Criteria

All patients must have a diagnosis of severe asthma, be taking high dose inhaled corticosteroids (GINA step 4 & 5), and be aged 16 years or over.

2.6.2 Exclusion Criteria

Patients that are unwilling to participate will be excluded from the study.

In the opinion of the physician responsible for the care of the patient, the patient has a condition, other than asthma, which is significantly contributing to their respiratory symptoms, e.g. lung cancer, heart failure or severe COPD.

The SAQ is currently only translated into British English. Therefore, if the participant is unable to read in English, they will be unable to participate.

2.6.3 Sample size calculation

Sample size determination is based on the analysis where the greatest number of patients is needed, namely factor analysis. For exploratory factor analysis the number of participants needed per item varies but ranges between 15 and 20 participants per item [18, 19]. There are 16 items in the SAQ. Thus, data from 240 – 320 participants is needed for any factor analysis, (80 – 107 participants from each centre.)

2.7 Data Collection Method

After providing written informed consent, participants will be provided with a pack consisting of a consent form, and the following questionnaires: (a) SAQ, (b) MiniAQLQ, and (c) EQ-5-5L (d) ACT/ACQ.

All clinic data will be input onto the Baseline Case Report Form (CRF) (Appendix 9) by a research nurse. This data and the completed pseudonymised questionnaires will be emailed to the Plymouth RA (JL) via NHS email. This data will utilise a participant number system. Each site will place a copy of the completed questionnaires into the patient's notes as they may contain relevant clinical information for current and future treatment.

2.8 Analysis

Factor analysis of the SAQ A trial principal axis factor analysis with scree plot will be calculated. On the basis of factor loadings on the first factor, it will be decided whether it is legitimate to provide an overall score for the questionnaire. Using the scree plot to determine factor number, an oblique rotation will be carried out and interpretation of emerging factor loadings (from the pattern matrix) determined.

Correlations between questionnaires

Correlations between questionnaires will be calculated using Pearson Correlations.

Discriminant validity We will test for significant differences between the SAQ and other scales using a mixed design analysis of variance (one within and one between) where groups are defined in two ways (a) maintenance dose oral corticosteroids and (b) cumulative dose oral corticosteroids. The aim of this analysis is to investigate whether the SAQ has better discriminant validity than other scales. First the interaction term of the analysis of variance will be used to determine whether sensitivity differs across all groups. Second, because the SAQ is expected to be more sensitive to discrimination at the top end of prednisolone use, a mixed design analysis of variance will be conducted on the two highest doses of prednisolone only.

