3.6 Analysis

The SAQ provides two scores, the SAQ score which is the mean of all 16 domain specific items, and the SAQ-global score which is a single item score based on the SAQ-Global, which itself is based on a Borg scale [21]. Borg scales use multiple quantifiers at empirically derived points along the scale with the aim of achieving a ratio scale. In this analysis plan, the term SAQ will refer to both the SAQ score and the SAQ global score. Separate analyses will be carried out on the SAQ score and SAQ-global. Several analyses will be carried to ensure that the MCID concept is fit for purpose.

Data from 4, 8, 12 and 16 weeks will be compared to the data collected at week 0 (baseline), providing 4 change scores per patient. Patients can indicate any one of 5 levels of improvement in any of the four weeks, or, if there is no change or deterioration, up to 11 types of change. If patients report the same level of global rating of change at each of the four time points (e.g., they record 'a little better' at week 4 and 'a little better at week 8), the average SAQ change score will be calculated for that patient. This average will then be used as the SAQ change for that particular level of global rating of change. This procedure is followed so that each patient can contribute just one value to the population average of the SAQ change score at any level of global change, and which, in the case of the level of 'a little better' is used to calculate the MCID. We shall carry out three analyses to check on the validity of the MCID concept. If the checks come out positive, then the existing method of calculating the MCID (i.e., as the change in the SAQ that maps on to the global rating of change criterion of 'a little better) will be adopted.

If the checks are negative – i.e., suggesting some revision to the way the MCID concept is employed – then we will adapt the methodology in accordance with our findings.

What degree of change on the SAQ is associated with each of the 5 levels of improvement and 5 levels of deterioration on the global rating of change score?

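### Judging the overall SAQ score by first-factor loadings alone cannot tell one dimension from two moderately correlated burdens

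*Protocol*

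**What the plan says.** Section 2.8 of the protocol begins the factor analysis of the SAQ as follows: "A trial principal axis factor analysis with scree plot will be calculated". The decision on a total score comes next: "On the basis of factor loadings on the first factor, it will be decided whether it is legitimate to provide an overall score". The number of factors and the rotation come after it: "Using the scree plot to determine factor number, an oblique rotation will be carried out", with the pattern matrix then interpreted. Nothing in 2.8 says that a second factor, if found, would alter the decision on the total.

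Three other places bear on this:

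- Section 2.4.1 says that the SAQ "provides separate assessments of the effect of asthma symptoms and the effect of asthma medicines", while also presenting it as a combined measure of disease and treatment. It expects the MiniAQLQ and the ACT to follow symptom burden and to follow treatment burden much less or not at all.
- Section 2.6.3 bases the Part 1 sample size on this factor analysis: "There are 16 items in the SAQ", and the requirement "ranges between 15 and 20 participants per item".
- Section 3.6 fixes "the SAQ score which is the mean of all 16 domain specific items" as one of two scores for the MCID work. The other is the single-item SAQ-global, analysed separately.

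**The concern.** The first unrotated principal axis factor is the direction that takes up the most common variance. If two distinct groups of items are positively correlated, that direction runs between them and both groups load on it. High first-factor loadings are therefore expected under one dimension and also under two moderately correlated ones. They are weak evidence for a single score.

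The alternative is not remote here. The protocol itself describes a symptom burden and a medicine burden, and expects other scales to track one far more than the other. Whether one number can represent both is what the factor analysis should help to settle.

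At stake is the meaning of the 16-item mean. If an improvement of d points per item falls only on k of the 16 items, the mean moves by d × k/16: half of d for 8 items, a quarter of d for 4. One MCID on the total could then stand for quite different changes in the two burdens.

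**Working it through.** **1. The plan's own figure.** Section 2.6.3: 16 × 15 = 240 and 16 × 20 = 320. Over three centres, 240/3 = 80 and 320/3 = 106.7, rounded up to 107. The upper total of 321 in section 2.3 is 107 × 3. The stated figures reproduce, and the check below uses N = 240.

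**2. Inputs.** From the protocol: 16 items, N = 240, principal axis factoring, decision from first-factor loadings. Assumed, because the protocol does not give them: item loading λ (0.6, 0.7, 0.8); correlation φ between two true factors (0 to 0.7); item split (8/8, 10/6, 12/4); and a pass defined as all 16 items at or above 0.3 (or 0.4) on the first unrotated factor of a two-factor extraction.

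**3. Population loadings.** For groups of n1 and n2 items, let μ = (n1+n2)/2 + √[((n1−n2)/2)² + φ²·n1·n2]. The unit vector (a, b) is proportional to (φ√(n1·n2), μ − n1). First-factor loadings are λ√μ·a/√n1 in group 1 and λ√μ·b/√n2 in group 2. For an even split this reduces to λ√((1+φ)/2).

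- 8/8, λ = 0.7, φ = 0.5: 0.7 × √0.75 = 0.61 on every item. At φ = 0.3: 0.7 × √0.65 = 0.56.
- 10/6, λ = 0.7, φ = 0.5: 0.66 and 0.52.
- 12/4, λ = 0.7, φ = 0.5: μ = 8 + √(16 + 12) = 13.29, vector proportional to (3.46, 1.29), so b = 0.349. The smaller group loads 0.7 × 3.646 × 0.349/2 = 0.45, the larger 0.69.

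All exceed 0.4, although two factors generate the data.

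**4. Simulated pass rates.** N = 240, 200 samples per setting, λ = 0.7, cut 0.3:

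| Split | φ = 0 | 0.2 | 0.3 | 0.5 | 0.7 |
|---|---|---|---|---|---|
| 8/8 | 0.26 | 0.96 | 1.00 | 1.00 | 1.00 |
| 10/6 | 0.00 | 0.27 | 0.69 | 1.00 | 1.00 |
| 12/4 | 0.00 | 0.02 | 0.20 | 0.96 | 1.00 |

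The Monte Carlo standard error near 0.955 is √(0.955 × 0.045/200) = 0.015.

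**5. Sensitivity at φ = 0.5** (in the order 8/8, 10/6, 12/4).

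- λ = 0.7, cut 0.4: 1.00, 0.89, 0.57.
- λ = 0.6, cut 0.3: 0.99, 0.94, 0.71.
- λ = 0.8, cut 0.3: 1.00 for all three.

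**6. Is the second factor visible?** The second eigenvalue of the sample correlation matrix exceeded 1 in every sample of every setting. Its population value at φ = 0.5 lies between 1.6 and 2.9. In a further 300 samples per setting (8/8, λ = 0.7, φ = 0.3 and 0.5), parallel analysis found two factors every time. The data would reveal the second factor, but the stated rule does not use that information.

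**The case against.** The strongest reply is that the rule is far from empty. A reader might infer that it can hardly ever fail, and the figures do not support that. With a 12/4 split and φ = 0.2, only 0.5-6.5% of samples pass a 0.3 cut across the three loading values. With uneven splits and uncorrelated factors none pass. At λ = 0.6, φ = 0.3 and an even split, about 31% pass a 0.4 cut. An even split is also the case most favourable to the criticism.

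A reader might also infer that the SAQ items are known to form two clusters. They are not: the questionnaire is not in the text available, section 2.4.1 also calls the SAQ a combined measure, and the item split is an inference.

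Nor is a second factor ignored altogether. The scree plot and the rotation would show it, and describing the factor structure is an objective in section 2.2. The 16-item mean is not the only score carried forward, because SAQ-global is analysed separately. Section 3.6 also allows item weighting in the MCID, though from correlations with the global rating of change and not from the factor structure.

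Finally, a loading cut-off may well sit in a statistical analysis plan, so its absence is no fault. A scree plot is a standard tool, and nothing here shows it giving a wrong factor number.

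All of this stands, and it narrows the point. It does not meet the core: the protocol names the quantity that decides, and that quantity does not compare one dimension with two.

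**Conclusion.** The concern holds in a limited form. Section 2.8 rests the overall score on first-factor loadings alone, and these do not distinguish one dimension from two moderately correlated burdens. With item loadings of 0.7 or 0.8 and factors correlated 0.5 or more, about 95-100% of two-factor samples of 240 would pass an assumed 0.3 cut, for all three splits. With weaker correlation and uneven splits the rule often fails, as it should (2-69% pass at λ = 0.7 and φ of 0.2 or 0.3).

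The size therefore depends on loadings, factor correlation, split and cut-off, none of which the protocol gives. That the criterion is blind to a moderately correlated second factor does not depend on the exact values. The consequence is that passing the rule would be weak support for the 16-item mean, which section 3.6 uses for the MCID without making it conditional on the factor result. It does not follow that the mean is wrong.

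**What to change.** In section 2.8:

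- Set the number of factors by parallel analysis (95th percentile), keeping the scree plot as illustration.
- Base the overall-score decision on that number and on the oblique solution (the factor correlation and a one- versus two-factor comparison), as well as on first-factor loadings.
- If more than one factor is retained, report subscale scores alongside the total and do not claim unidimensionality.

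In section 3.6, refer to that result and, if more than one factor is retained, report SAQ change by subscale alongside the total.

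A fixed cut-off on omega-hierarchical, such as 70%, should not be used. With only two factors it is not identified unless equal second-order loadings are assumed. For 8/8 and λ = 0.7, total-score variance is 2 × 5.6² × (1+φ) + 16 × 0.51. At φ = 0.6 that is 108.5. Equal second-order loadings give (16 × 0.7 × √0.6)² = 75.3, or 0.69; loadings of 1 and φ give (5.6 × 1.6)² = 80.3, or 0.74. The same correlations fall on both sides of 70%. At φ = 0.3 the two values are 0.42 and 0.59.

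The cost is a few sentences and slightly more analysis, with standard software on the same data. The single score may turn out to be less strongly supported.

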2.2 Objectives

To collect data from patients attending the UK specialist Asthma centres:

To provide a description of the factor structure of the SAQ and to demonstrate equivalence across populations.

To show that the SAQ correlates in an acceptable manner with the Mini Asthma Quality of Life Questionnaire (MiniAQLQ) and EQ-5D-5L (EQ5D)

To show that the SAQ is a discriminator of patients who have different frequencies of exacerbations and different levels of prednisolone consumption.

To show that the SAQ is equivalent in discrimination for exacerbations to the MiniAQLQ or EQ5D but is a better discriminator than these questionnaires for treatment levels of oral corticosteroids.

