The mean, confidence intervals, and standard deviation of change of the SAQ will be calculated for each level of change in the GRCQ. These means will then be plotted (change in SAQ on x axis, global change on y axis) to show the relationship between change and perceived change at different degrees of change. These results should show that the change in the SAQ increases with increase in global change scores, and will be tested for by analysis of variance. This analysis is needed to show that the MCID is specific to the level of change of 'a little better' or 'a little worse' rather than any other level of global rating of change. The analysis will also check whether 'a little better' is equivalent in terms of 'a little worse' in terms of SAQ change.

Is the MCID transitive – i.e., is the MCID independent of level of deficit of quality of life?

Patients will be allocated to quartiles based on severity of the SAQ score at week 0. The mean, confidence intervals and standard deviation of change scores for change at 'a little better' will be calculated. Analysis of variance will be calculated for the four quartiles to test of transitivity. Effect size (eta) will be calculated. This analysis is needed to show that the MCID level can be applied across the full range of deficit of quality of life.

Are items in the SAQ equivalent with regard to the MCID – i.e., is change in all the 16 SAQ items equivalent in terms of their relationship with the global rating of change?

To test for equivalence, change in each of the 16 items of the SAQ and the SAQ-global will be correlated against the global rating of change score. These correlations will be examined and interpreted. Regression will be explored, but may be ruled out due to co-linearity. This analysis is needed to show whether weighting of items is needed when calculating the MCID, or whether the MCID is based simply on the mean of all items.

Demographic information analyses

In addition, we will also test whether baseline characteristics are similar across the four quartile groups and investigate whether the change in SAQ is related to the collected demographic and clinical data.

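### The two exacerbation objectives in Protocol 2.2 have no matching analysis in 2.8, which groups patients only by oral corticosteroid dose and tests only for differences

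*Protocol*

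**What the plan says.** Section 2.2 of the Protocol has two discrimination objectives, each with an exacerbation part and an oral corticosteroid (OCS) part.

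- The first begins "To show that the SAQ is a discriminator of patients who have different frequencies of exacerbations" and goes on to prednisolone consumption.
- The second begins "To show that the SAQ is equivalent in discrimination for exacerbations to the MiniAQLQ or EQ5D" and then claims that the SAQ does better than those scales for OCS treatment level.

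Section 2.4.2 lists, among the clinic data outcome measures, "Number of exacerbations in the last 12 months requiring OCS".

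The discriminant validity paragraph of section 2.8 describes the method: "We will test for significant differences between the SAQ and other scales using a mixed design analysis of variance". On the between-patient factor it says "groups are defined in two ways (a) maintenance dose oral corticosteroids and (b) cumulative dose oral corticosteroids". Its purpose is given as "The aim of this analysis is to investigate whether the SAQ has better discriminant validity than other scales". The first step is: "First the interaction term of the analysis of variance will be used to determine whether sensitivity differs across all groups". The second step repeats the analysis on the two highest prednisolone doses. The rest of 2.8 covers factor analysis and Pearson correlations between questionnaires.

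**The concern.** The comparative case for the SAQ has two halves: as good as existing scales on exacerbations, and better on OCS burden. Section 2.8 provides for the second half only. The first half fails on two counts.

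- **Grouping.** No analysis divides patients by exacerbation frequency, so even the simple objective that the SAQ discriminates on it is not tested.
- **Type of inference.** An equivalence objective is paired with a difference test whose stated aim is superiority. If exacerbation groups were put into the same analysis of variance and a non-significant interaction were read as equivalence, a real shortfall of the SAQ could pass as equal performance.

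**Working it through.** **Objectives against analyses**

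| Objective (2.2) | Grouping in 2.8 | Inference in 2.8 |
|---|---|---|
| SAQ discriminates by exacerbation frequency | none | none |
| SAQ equivalent to MiniAQLQ or EQ5D for exacerbations | none | none; difference test only |
| SAQ discriminates by prednisolone level | maintenance and cumulative OCS dose | difference test |
| SAQ better than the others for OCS level | maintenance and cumulative OCS dose; two highest doses | difference test, aim is better discrimination |

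Three other places might fill the empty rows, but do not.

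- The correlations in 2.8 are between questionnaires, not with exacerbations.
- Cumulative OCS dose takes in courses given for exacerbations, but it is a dose variable. Section 2.2 also sets opposite hypotheses for exacerbations (equivalent) and OCS level (better), so one variable cannot stand for both.
- Section 3.6 has a step that opens "To test for equivalence, change in each of the 16 items of the SAQ". It correlates item changes with the global rating of change in Part 2, with no margin and no exacerbation grouping.

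**Sample size**

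The stated Part 1 figure reproduces. Section 2.6.3 gives 16 items at 15–20 participants each: 16×15 = 240 and 16×20 = 320. Per centre this is 240/3 = 80 and 320/3 = 106.7, rounded up to 107; 3×107 = 321, as in 2.3. The figure rests on factor analysis. No margin or power is given for the discrimination comparison.

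**Why a non-significant interaction does not show equivalence (illustration)**

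Inputs from the Protocol: N = 240–321 for Part 1 (2.3), with 280 taken as mid-range. Section 3.2 adds Part 2 baseline questionnaires to the Part 1 dataset. With the 100 patients of 3.4.3, N = 340–421. With the 30–50 at each of five sites in 3.2 (150–250), N = 390–571.

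Assumed inputs: two equal exacerbation groups, scores in SD units, between-scale correlation ρ = 0.7, true gap in discrimination 0.2 SD, normal approximation.

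With two scales and two groups, the interaction is a two-sample comparison of within-patient differences:

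SE = √(2(1−ρ)) × √(1/n₁ + 1/n₂)

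At N = 280: SE = √0.6 × √(2/140) = 0.7746 × 0.1195 = 0.0926. Then 0.2/0.0926 = 2.16, and P(non-significant at two-sided 5%) = Φ(1.96 − 2.16) = 0.42. The 90% confidence interval half-width is 1.645 × 0.0926 = 0.15 SD.

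| N | SE | P(non-significant), true gap 0.2 SD | 90% CI half-width (SD) |
|---|---|---|---|
| 240 | 0.100 | 48% | 0.16 |
| 280 | 0.093 | 42% | 0.15 |
| 321 | 0.086 | 36% | 0.14 |
| 340 | 0.084 | 34% | 0.14 |
| 421 | 0.076 | 25% | 0.12 |
| 571 | 0.065 | 13% | 0.11 |

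Over N = 240–321 and ρ = 0.6–0.8 the probability runs from 19% to 59%. A 70/30 split at N = 280 and ρ = 0.7 raises 42% to 49%.

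**What an equivalence rule would cost**

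With no true gap, the chance that the 90% interval falls within ±m is 2Φ(m/SE − 1.645) − 1. At N = 280 and ρ = 0.7 this is 39% for m = 0.20, 71% for m = 0.25 and 89% for m = 0.30. For m = 0.20 it is 54% at N = 340 and 85% at N = 571. These margins are assumptions; the Protocol gives none.

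**The case against.** **The list of groupings may not be meant as complete.** The two groupings belong to one analysis, whose declared purpose is the superiority question, and OCS dose suits that purpose. A reader might infer that 2.8 rules out an exacerbation analysis. It does not say so, and a statistical analysis plan may exist. Cut-points and a margin are commonly set there. This narrows the point to an omission and a mismatch. It does not remove it, because the Protocol has its own analysis section, and the only discrimination method named there cannot support a stated equivalence objective.

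**A later analysis and section 5.2.** A reader might infer that an exacerbation analysis would have to be reported as additional under that section. This depends on what the original statistical plan contains, which is not shown, so it is not supported.

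**The word equivalent may be loose.** Section 2.2 also uses equivalence for factor structure across populations, 3.6 uses it for a set of correlations, and 5.2 says the study is not a trial. A margin-based reading is therefore not the only one. This is a fair reason to allow rewording as an alternative to a margin.

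**Raw scores.** A reader might also infer that the interaction is invalid because the scales have different metrics. The Protocol does not say that raw scores will be used, so this is not an error in the text.

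**The figures.** They test a misuse that the Protocol does not propose, with assumed inputs, and the Part 1 range leaves out Part 2 baselines. Including them lowers the 42% to 13–34%. Section 3.3.2 does not list a 12-month exacerbation count at the Part 2 baseline, although 3.5 uses the same baseline form, so that gain is uncertain.

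**Conclusion.** The point holds as a mismatch between 2.2 and 2.8, and should be fixed. Neither exacerbation objective has a matching analysis, and the one comparative method described tests for differences with a superiority aim. This rests on the text alone and does not depend on any assumed figure.

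The numbers only show why a non-significant interaction would be weak evidence of equivalence. With ρ = 0.7 and two equal groups, a true 0.2 SD gap would be non-significant in about 42% of studies at N = 280. At N = 340–571 the figure is about 13–34%, if Part 2 baselines are added and have exacerbation counts. The OCS objectives and the data collection are not affected.

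**What to change.** Add to 2.8 a grouping by the 12-month exacerbation count already collected under 2.4.2, and test SAQ discrimination across it. For the comparison with the MiniAQLQ or EQ5D, choose one of two routes:

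- **(i) Keep the equivalence objective.** Claim equivalence only if the 90% confidence interval for the paired difference in standardised group effect lies within a prespecified margin.
- **(ii) Reword the objective in 2.2** as an estimated comparison, reported with its confidence interval.

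The cost is a few sentences and a little more analysis, with no new Part 1 data. Under (i) equivalence becomes harder to claim: at N = 280, ρ = 0.7 and equal groups, a margin below about 0.15 SD could not be met. Route (ii) avoids this but gives up the word equivalent.

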been increasing interest in identifying people at risk of asthma deaths, improving services for patients with severe asthma, and rational use of new treatments.

The SAQ questionnaire was derived from a qualitative study [8] and questions and design were evaluated by a panel of international expert clinicians. The concepts and wording were modified and tested in an iterative series of four focus groups of patients attending the difficult asthma service [9]. The questionnaire was then field tested in 160 patients and compared to the MiniAQLQ, the Asthma Control test and clinic data including BMI, lung function, and health care consumption [10]. The final version takes into account the lessons learned from this quantitative study and further input from the panel of experts.

The SAQ questionnaire has 16 questions rated on a 0-6 Likert scale and on a 0-100 scale rating of (i) overall quality of life (ii) how your asthma symptoms and the side effects of your medicines have affected your quality of life during the last two weeks.

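### The scale-by-group interaction that section 2.8 uses to judge better SAQ discrimination depends on each scale's spread and direction unless the scores are first put on a common metric.

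*Protocol*

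**What the plan says.** Protocol section 2.2 makes it a Part 1 objective to show that the SAQ, set against the MiniAQLQ and EQ5D, "is a better discriminator than these questionnaires for treatment levels of oral corticosteroids". Section 2.8 repeats this purpose: "The aim of this analysis is to investigate whether the SAQ has better discriminant validity than other scales". The method is given as "We will test for significant differences between the SAQ and other scales using a mixed design analysis of variance (one within and one between"), with groups formed by maintenance dose and by cumulative dose. The deciding quantity is named: "First the interaction term of the analysis of variance will be used to determine whether sensitivity differs across all groups". In a second step, "a mixed design analysis of variance will be conducted on the two highest doses of prednisolone only".

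The instruments differ in format. Section 1.1: "The SAQ questionnaire has 16 questions rated on a 0-6 Likert scale and on a 0-100 scale rating". On the EQ-5D-5L, section 2.4.1 says: "This is a 5-item scale, with a final question which asks patients to use a category rating scale". The same section describes the ACQ as scored 0 to 6 with 6 the worst state. It gives no range for the MiniAQLQ and does not say which EQ-5D-5L score is analysed. Nothing in the document puts the scales on a common metric or in a common direction before the analysis of variance.

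**The concern.** With questionnaire as the within-patient factor, the interaction asks whether the difference in mean score between corticosteroid groups is the same number of points on every scale. A scale with a larger SD shows a larger gap in points for the same ability to separate groups. Two equally discriminating scales with different SDs therefore give a non-zero interaction. A scale that runs the opposite way gives one too.

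At stake is a stated Part 1 conclusion, superiority over the MiniAQLQ and EQ5D for corticosteroid treatment level. Run in its ordinary form, the test could report a difference in sensitivity that does not exist, miss one that does, or credit the wrong scale.

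**Working it through.** **The plan's own figure.** The only figure attached to Part 1 is the sample size in section 2.6.3: 15 × 16 = 240 and 20 × 16 = 320; 240/3 = 80 and 320/3 = 106.7, rounded to 107 per centre. It reproduces and is not in dispute. No figure is attached to the interaction test.

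**Inputs.** N = 240 is from the protocol. The following are assumptions, because the document gives none of them: four equal groups with evenly spaced means; d = highest versus lowest group in SD units, the same on both scales, so that there is no true difference in discrimination; correlation between scales r = 0.7; two-sided 5% test; two scales compared at a time.

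**Formula.** With two scales, the interaction F equals a one-way ANOVA F on the within-patient difference. Let R be the ratio of the two SDs. Group means lie at -1/2, -1/6, 1/6 and 1/2 of the range, so their mean square is (1/4 + 1/36 + 1/36 + 1/4)/4 = 5/36. The noncentrality is

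λ = N × (5/36) × d² × (R - 1)² / (R² + 1 - 2rR), on 3 and 236 df (critical F = 2.64).

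Example, R = 2 and d = 0.5: 240 × 5/36 × 0.25 = 8.33; (2 - 1)²/(4 + 1 - 2.8) = 0.4545; λ = 3.79; rejection rate 33.6%.

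**All-group analysis: false rejection with equal discrimination.**

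| SD ratio R | d = 0.3 | d = 0.5 | d = 0.8 |
|---|---|---|---|
| 1 | 5% | 5% | 5% |
| 1.17 | 6% | 7% | 10% |
| 1.5 | 9% | 17.5% | 41% |
| 2 | 14% | 34% | 74% |
| 3 | 20% | 49% | 91% |
| 4.8 (e.g. SD 1.2 vs 0.25, a 0-1 index) | 23% | 58% | 95% |
| 16.7 (e.g. SD 1.2 vs 20, a 0-100 score) | 26% | 65% | 98% |

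Simulation at d = 0.5 agrees for the last two rows (58% and 65%) and gives about 5% once each scale is standardised.

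**Sensitivity (d = 0.5, ratios 4.8 and 16.7).** 53-66% for r from 0.5 to 0.9; 72-79% at N = 321; 73-79% with three groups; 48-54% with five; 52-58% with groups split 50/20/20/10.

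**Two-highest-dose step.** On the same linear trend the gap is d/3. At ratios 4.8 and 16.7 and d = 0.5, false rejection is 13-14% with 60 per group and 9-10% with 30. At d = 0.8 it is 26-30% and 15-17%. At ratios up to 1.17 it is 5-6%.

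**Hidden advantage.** SAQ truly better (0.8 vs 0.4 SD), SDs 1.2 vs 20. In points the SAQ gap is 0.8 × 1.2 = 0.96 and the comparator's is 0.4 × 20 = 8. The unstandardised interaction favours the SAQ in about 0.1% of runs, against about 70% after standardising.

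**Reversed verdict.** SAQ truly worse (0.4 vs 0.8 SD), SDs 1.2 vs 0.25. In points the gaps are 0.4 × 1.2 = 0.48 and 0.8 × 0.25 = 0.20. The unstandardised interaction favours the SAQ in about 22% of runs, against under 0.1% after standardising.

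**Direction alone.** Equal SDs, equal |d| = 0.5, N = 320, one scale reversed (r = -0.7): λ = 320 × 5/36 × 1² / (1 + 1 + 1.4) = 13.07, and rejection is 87%.

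**Units alone.** In one simulated dataset, multiplying the SAQ by 100/6 left its own group F at 11.08 but moved the interaction F from 1.47 (p = 0.22) to 10.58 (p about 0.000001).

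**The case against.** The strongest reply is that score preparation is ordinary SAP detail. Section 2.8 does not say that unscaled scores will be used, and the fix keeps the same model, the same interaction and the same second step. A reader might infer that the protocol commits to raw scores; it does not, and an unseen SAP may standardise. What remains is that the protocol itself chooses the deciding term for scales it describes in unlike formats, and that this term measures discrimination only once a metric is fixed. That is a weakness in the stated test as well as an absent detail.

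A reader might also infer that the SAQ score is undefined, because section 2.8 says of the factor loadings that "it will be decided whether it is legitimate to provide an overall score for the questionnaire". The document does not support that. Section 3.6 defines the SAQ score as the 16-item mean and SAQ-global as a separate single-item score. It does so for Part 2, but the definitions exist.

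Three further limits stand:
- The high error rates need an SD ratio far from 1, as with an EQ-5D-5L index or a 0-100 score. For the MiniAQLQ, whose range is not given, the SD may be close to the SAQ's and the effect slight.
- The only direction the protocol states is the ACQ's, and the ACQ is not a comparator in the section 2.2 discrimination objective, although the reference to other scales in section 2.8 is not limited to those comparators.
- The rates are for pairwise comparisons. A within factor with three or more scales was not calculated.

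**Conclusion.** The concern holds: on scores in their own units, the named interaction answers a question about points, and its result depends on spread and direction as well as discrimination. That dependence needs no assumption.

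Its size does. Every rate rests on assumed SDs, correlation, group structure and effect size. The 58-65% figures illustrate a comparator on a very different metric and should not be read as the error rate expected in this study. The effect nearly vanishes at similar SDs (7% at a ratio of 1.17, d = 0.5) and is modest in the two-highest-dose step at d = 0.5. It would grow there if the top two dose groups lay further apart than the assumed third of the range.

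The point should be fixed, because it can change a stated Part 1 conclusion. It does not touch the sample size or the data collected.

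**What to change.** In section 2.8, state that before the mixed analysis of variance all scales are aligned in one direction and each is divided by its pooled within-group SD. Test the interaction on those scores in both the all-group and the two-highest-dose analyses. Report the difference in standardised group effects between the SAQ and each comparator, with a confidence interval. Use the SAQ score and SAQ-global as section 3.6 defines them, and name the EQ-5D-5L score entered.

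The cost is a few sentences of wording and slightly more analysis work, with no change to design or data.
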